14.2.2. Study Design and Interim Analysis

The primary objective of this study is to evaluate the overall response rate to the combination of anti-PD1 therapy and duvelisib. We would consider the combination futile and not worth further study if the response rate is 5% or lower. We will monitor the efficacy of the regimen using a Bayesian method. We will consider the trial futile and propose stopping if the posterior probability that response rate is <5% given the observed data is >70%. A non-informative prior of Beta (0.5, 0.5) is used for the true response rate and the cohort size is set to be 5. The futility early stopping boundaries are given in the following table:

# Patients (inclusive)	# Responses (inclusive) are considered futile	Actions
5	Never stop with this many patients	
10	Never stop with this many patients	
15	0	Early stopping
20	0	Early stopping
25	0	Early stopping

Therefore, if none of the first 15 patients responds to the combination, the study will be stopped early for futility. Otherwise, the study will continue to recruit all 30 patients. By the end of the study, we will consider the study combination effective and worth further study if the posterior probability that the response rate is $>5\%$ given the observed data is 90% or higher (in our case, if we observe >3 responses in 30 evaluable patients). The following figure demonstrated the simulation results of the operating characteristics of our study design, under the assumption of various true response rates. As shown, when the response rate is 5% or lower, the probability of early stop is higher (>0.46) and probability of declaring efficacy (i.e. “type I error”) is low (<0.06). When the response rate is 20% or higher, the probability of early stopping is less than 3.5% and the probability of declaring efficacy (i.e. “power”) is over 86%.

The simulation is performed using the web tool for Bayesian Efficacy Monitoring Via Posterior Probability (<http://www.trialdesign.org/one-page-shell.html#BEMPO>).

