14.0 Statistical Methods

This clinical trial includes a phase I dose-finding study and a phase II efficacy study. The phase I portion requires up to 18 patients. The phase II portion needs an additional 24 patients (6 carried over from phase I using the RP2D level) for a study total of up to 42 patients and a phase II total of 30 patients. With 2 centers, each accruing 1-2 patients per month, we anticipate completing enrollment in 18 months.

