14.2. Phase II Portion of the Study

The study primary endpoint will be analyzed once the last patient on treatment is on study for 18 weeks.

14.2.1. Study Populations:

Safety population: patients who received any amount of the study regimen.

[figure not shown]
Efficacy population: patients who received at least one cycle of the treatment and at least one efficacy evaluation.

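### The Phase II success rule has no cut-off below 30 evaluable patients; applied as written at 28, it accepts 3 responses and the type I error rises from 0.058 to 0.151

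*Combined protocol and SAP*

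**What the plan says.** Section 14.2.2 takes a response rate of 5% as the null: the combination is "futile and not worth further study if the response rate is 5% or lower". The prior and the interim schedule are given together: "A non-informative prior of Beta (0.5, 0.5) is used for the true response rate and the cohort size is set to be 5". The futility table stops the trial for no responses at 15, 20 or 25 patients. At the end, success is a posterior probability of a rate above 5%, "given the observed data is 90% or higher (in our case, if we observe >3 responses in 30 evaluable patients"). The section reports a type I error below 0.06 and early stopping above 0.46 at a 5% rate. At a 20% rate it reports power above 86% and early stopping below 3.5%.

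Section 14.0 plans "for a study total of up to 42 patients and a phase II total of 30 patients", six of the 30 being carried over from Phase I. Section 14.2.1 defines the efficacy population as "patients who received at least one cycle of the treatment and at least one efficacy evaluation". Section 12.1 separately ties evaluability for response to re-evaluation at 12 weeks, with an exception for objective progression before the end of cycle 1. Neither section 14.0 nor 14.2 allows for non-evaluable Phase II patients, addresses their replacement, or gives a cut-off for fewer than 30.

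**The concern.** A fixed posterior threshold becomes a different response count as the number of patients changes. The plan gives the count, and the operating characteristics, for 30 only. Yet its own efficacy population drops anyone who does not complete a cycle or has no efficacy evaluation. The first scheduled scan is at 12 weeks (5.3), so a patient who leaves early for toxicity, withdrawal or clinical decline may never have one.

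If the final number falls far enough for the required count to step down by one, a trial that has lost patients passes on fewer responses. This is the go/no-go rule for the primary endpoint. With 3 responses in 28 patients (10.7%), someone applying the posterior would call the combination effective and someone holding to the printed count would not. The plan does not say which governs, so the choice could be made after the data are known.

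**Working it through.** **Inputs, all from 14.2.2.** Prior Beta(0.5, 0.5); success if Pr(rate > 0.05 | data) ≥ 0.90; futility stop at 0 responses in 15, 20 or 25; null rate 5%; target rate 20%. The futility looks are taken to fall at 15, 20 and 25 evaluable patients.

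**Formulas.** After x responses in n patients the posterior is Beta(0.5 + x, 0.5 + n − x). The bar t is the smallest x for which its upper tail above 0.05 is at least 0.90. A trial with a response among the first 15 patients can never show zero later, so only the look at 15 can stop it. For true rate p,

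P(declare) = P(X_n ≥ t) − (1 − p)^15 × P(X_{n−15} ≥ t), with X binomial.

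**The plan's own figures first (n = 30).** Three responses give a posterior of 0.8898 (fail) and four give 0.9683 (pass), so the bar is 4, as printed.
- Early stop at 5%: 0.95^15 = 0.4633 (stated >0.46).
- P(declare) at 5%: 0.0608 − 0.4633 × 0.0055 = 0.0582 (stated <0.06).
- P(declare) at 20%: 0.8773 − 0.0352 × 0.3518 = 0.8649 (stated >86%).
- Early stop at 20%: 0.80^15 = 0.0352 (stated <3.5%; the gap is within simulation error).

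**The same rule at n = 28.** Three responses give 0.9078, so the bar is 3. P(declare) at 5% is 0.1627 − 0.4633 × 0.0245 = 0.1513.

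**By final evaluable number:**

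| n | Posterior at 3 responses | Bar under the 0.90 rule | P(declare) at 5% / 20% | With bar held at 4: at 5% / 20% |
|---|---|---|---|---|
| 30 | 0.8898 | 4 | 0.058 / 0.865 | 0.058 / 0.865 |
| 29 | 0.8990 | 4 | 0.053 / 0.849 | 0.053 / 0.849 |
| 28 | 0.9078 | 3 | 0.151 / 0.921 | 0.048 / 0.831 |
| 27 | 0.9163 | 3 | 0.141 / 0.913 | 0.043 / 0.811 |
| 26 | 0.9243 | 3 | 0.132 / 0.903 | 0.038 / 0.788 |
| 25 | 0.9320 | 3 | 0.122 / 0.890 | 0.034 / 0.762 |
| 20 | 0.9641 | 3 | 0.075 / 0.792 | 0.016 / 0.588 |

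The bar is 3 for every n from 17 to 28. At 16 it falls to 2 (posterior 0.9057), but a loss of that size is remote from the plan.

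**How likely is a final number of 28 or fewer?** The documents give no rate of non-evaluability. Assume that each of 30 patients is non-evaluable independently with probability q, unrelated to response. Then P(at least 2 lost) = 1 − (1 − q)^30 − 30q(1 − q)^29. Averaging the type I error over the resulting n gives:
- q = 2%: P(at least 2 lost) 0.12, average type I error 0.067.
- q = 5%: 0.45 and 0.095.
- q = 10%: 0.82 and 0.121.

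**The case against.** The best defence is that nothing is wrong at the design size. The posterior is the single criterion, and the count is a worked instance tied expressly to 30 evaluable patients. A reader might infer that 14.2.2 contains two contradictory rules. The text does not support that, because the two agree at 30 and at 29 and the quoted operating characteristics are right. What stands is that nothing is specified for 28 or fewer.

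A reader might also infer that the plan fixes Phase II at 30 and forbids replacement. It does neither; it is silent. The mention of 30 evaluable patients could be read as a target to be reached by enrolling further patients, and on that reading the problem disappears unless accrual ends short. But 14.0 plans a Phase II total of 30 with no allowance, and 14.2.2 speaks of recruiting 30. If replacement is meant, it has to be written.

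It is fair, too, that the plan sets no formal type I error limit. It reports <0.06 as a simulated property, and the step at 28 comes from the discreteness of the binomial under a fixed posterior threshold. That explains the step. It does not rescue the figure offered to justify the design, which fails under the stated rule once two patients drop out.

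Finally, holding the bar at 4 costs power. That objection stands in full.

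**Conclusion.** The concern holds, conditionally. If the final evaluable number is 30 or 29, the rule behaves as described. If it is 28, the posterior rule lowers the bar from 4 responses to 3, and the probability of declaring efficacy at a true 5% rate is 0.151, about 2.6 times the 0.058 at 30. It would be wrong to read 0.15 as the error whenever patients are lost. It is the value at exactly 28, falling to 0.122 at 25 and 0.075 at 20. Averaged over assumed non-evaluability of 2% to 10% it is 0.067 to 0.121, still above the stated 0.06.

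The conclusion rests on three conditions: the posterior form governs, non-evaluable patients leave the denominator as 14.2.1 allows, and they are not replaced. The plan permits all three.

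**What to change.** In 14.2.2, state that success requires at least 4 responses whatever the final evaluable number up to 30. Raising the posterior cut-off from 0.90 to 0.95 is equivalent for n = 23 to 30: 3 responses reach at most 0.946 (at 23) and 4 reach at least 0.968 (at 30). The decision at 30 is unchanged.

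Alternatively, in 14.2.1, fix the denominator at 30 by counting treated non-evaluable patients as non-responders. This also holds the bar at 4, but does not cover accrual that ends short of 30.

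With either, say in 14.0 whether non-evaluable Phase II patients are replaced, and add to 14.2.2 a short table of type I error and power by evaluable number.

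The cost is a sentence and a table, plus a disclosure. With the bar at 4, power at a 20% rate is 0.849 at 29, 0.831 at 28, 0.811 at 27, 0.788 at 26 and 0.762 at 25, so the stated 86% holds only at 30. The plan should say so.

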14.2.3. Analysis of Primary and Secondary Endpoints

14.2.3.1. Analysis of Tumor Response:

Overall Response Rate (**primary endpoint**) will be estimated by the proportion of patients with a best response of complete response (CR) or partial response (PR) by RECIST 1.1 criteria, with corresponding exact 95% confidence limits being reported. The response rate will also be compared between pre-

specified subsets of melanoma patients with Fisher's exact tests. These comparisons will be done in an exploratory manner.

The distribution of response duration (defined in Section 12.3.4) will be characterized by median and quartiles, with the corresponding Kaplan-Meier estimate being made of PFS among patients responding to treatment. To the extent possible from the available data, proportional hazards models will be used to assess whether the rate of disease progression varies materially among the three subgroups of disease response: CR, PR, and SD.

14.2.3.2. Analysis of Progression Free Survival (PFS) and Overall Survival (OS):

PFS and OS (defined in Section 12.3.5 and 12.3.6 respectively) will be estimated by the Kaplan-Meier method. The corresponding median survival times (with 95% confidence limits) will be determined, as will the cumulative percentage of patients remaining progression-free (and the cumulative percentage-alive) at selected time points after initial treatment (e.g., 6,12, 18 months).

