3.2 Study Endpoints

3.2.1 Primary Endpoints

- Phase I
 - RP2D of duvelisib when used in combination with nivolumab, as determined by immunomodulatory effect in peripheral blood and TME, toxicity, and any early efficacy signals.
 - Maximum-tolerated dose of duvelisib in combination with nivolumab.

- Phase II
 - Overall response rate of the combination of anti-PD1 therapy and duvelisib as measured by overall antitumor response (defined as complete response + partial response) based on RECIST v1.1 criteria initially assessed at 12 weeks after initiation of the combination, compared to baseline imaging obtained immediately prior to initiating combination, and subsequently at 12 week intervals until progression.

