3.2.2 Secondary Endpoints

Several secondary endpoints will be analyzed as follows:

- Acute and late toxicities rates throughout treatment, as graded by CTCAE v5.0 in patients at each dosing interval and in the expansion cohort
- Clinical benefit of combination therapy, defined as complete response, partial response and stable disease as assessed by RECIST v1.1, initially assessed at 12 weeks after initiation of therapy and subsequently at 12-week intervals until progression

- Duration of response defined by time at which measurement criteria are first met for complete response or partial response until the first time at which progressive disease is objectively documented
- Progression-free survival defined as time at start of treatment and first date of documented progression or death due to any cause
- Overall Survival defined as the time of start of treatment and the date of death due to any cause. Patients who are alive will be censored at the time of the last follow-up. Patients will be followed for survival for 5 years.
- Safety of the combination of anti-PD1 and duvelisib measured by adverse events graded by CTCAE v5.0. Adverse events will be captured during treatment and 100 days after discontinuing treatment. We will continuously monitor for DLTs as defined in section 8.1 that are possibly, probably or definitely related to treatment. If the adverse event rate exceeds acceptable limits, the study will be modified or discontinued.
- Subset analysis will be performed to determine how certain disease characteristics affect response to the combination, including prior time prior to progression while on anti-PD1 therapy, presence of CNS disease, radiated CNS disease and tumor BRAF mutation status.

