6.7 Safety Evaluations

Will be conducted according to the table below.

Table 6.7.1: Schedule of Study Procedures

Study Stage	Screening	Intervention									Safety Follow-up
Visit Number		1	2	3	4-6	7	8-9	10	11-15	16+	
Study Days (+/- 1 week) For cycles 1-4, visits every 14days, then every 28 days	-28 to 0	1-14	15-28	29-42	43-	85-98	99-126-168	169-196	197-364	365+	
Cycle Number		C1D1 and 15	C2D1 and 15	C3D1 and 15	C4-6 Day 1 and C4D15	C7D1	C8-9D1	C10D1	C11-15D1	C16+D1	
Informed Consent/Assent	X										
Review Inclusion/Exclusion Criteria	X										
Demographics/Medical History	X										
Physical Examination	X	X	X	X	X	X	X	X	X	X	
Vital Signs: BP, HR, RR, Temp O2	X	X	X	X	X	X	X	X	X	X	
Height and BMI	X										
Weight	X	X	X	X	X	X	X	X	X	X	
Pregnancy Test	X										
Assess contraceptive use	X	X	X	X	X	X	X	X	X	X	
EKG	X										
Prior/Concomitant Medications – including PJP and VZV prophylaxis	X	X	X	X	X	X	X	X	X	X	
Laboratory Evaluation	X	X	X	X	X	X	X	X	X	X	
Peripheral blood for correlates (week 0, 4*, 12, at progression) *For phase I		X	X		X Cycle 4 only						
Diagnostic imaging (every 12 weeks +/- 7 days)	X				X		X		X		
Biopsy for correlates (baseline, 12 weeks +/- 2 weeks)		X			X Cycle 4 only						
Dispense Investigational Product (IP)		X	X	X	X	X	X	X	X		
IP Compliance		X	X	X	X	X	X	X	X		
Adverse Events and Unanticipated Problems Assessment		X	X	X	X	X	X	X	X	X	

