12.3.4 Duration of response

- Duration of overall response – The duration of overall response is measured from the time measurement criteria are met for CR or PR (whichever is first recorded) until the first date that recurrent or progressive disease is objectively documented. The duration of overall CR is measured from the time measurement criteria are first met for CR until the first date that progressive disease is objectively documented.

- Duration of stable disease - Stable disease is measured from the start of the treatment until the criteria for progression are met, taking as reference the smallest measurements recorded since the treatment started, including the baseline measurements.

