12.3.5 Progression-Free survival

- Progression-free survival defined as the time between the date of first treatment and the date of first documented progression or death due to any cause, whichever occurs first.

[figure not shown]

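### Section 14.2.3.1 pairs duration of response with a Kaplan-Meier curve of PFS among responders, which has a different start and a different event, and the duration definitions do not say how deaths are handled

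*Combined protocol and SAP*

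**What the plan says.** The analysis text is one sentence in Section 14.2.3.1. It opens "The distribution of response duration (defined in Section 12.3.4) will be characterized by median and quartiles" and continues "with the corresponding Kaplan-Meier estimate being made of PFS among patients responding to treatment".

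The definitions behind its two halves are these:

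- **Duration of response, Section 12.3.4.** The clock starts when CR or PR criteria are first met and runs "until the first date that recurrent or progressive disease is objectively documented".
- **Duration of response, Section 3.2.2.** Same start, running "until the first time at which progressive disease is objectively documented". Neither section mentions death or gives a censoring rule.
- **PFS, Section 12.3.5.** "the time between the date of first treatment and the date of first documented progression or death due to any cause".

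On timing, Section 3.2.1 has response "initially assessed at 12 weeks after initiation of the combination" and then at 12-week intervals. Table 6.7.1 allows 7 days either side. Sections 5.3 and 12.0 permit a scan before week 12 when deterioration or progression is suspected.

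**The concern.** The word linking the two halves of the sentence presents the PFS curve as the estimate that goes with response duration. It is not: its clock starts earlier and it counts an extra kind of event. A responder must also be progression-free up to the response, so the early part of a PFS curve among responders is event-free by selection. That guaranteed time says nothing about how long responses last.

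A responder still in response at the data cut has a censored duration, so the median and quartiles need a method for censored data. The only one the plan names for duration is this PFS curve. The synopsis does not list duration among the Kaplan-Meier analyses.

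Duration of response is a stated secondary objective and endpoint, and Section 4.4.1 foresees 3 years of data collection to determine it. As written, analysts working from the same data could report different medians and each cite the plan.

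**Working it through.** The plan states no figure for duration of response, so there is none to reproduce. The check has three steps.

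**1. Time origin (no distributional assumption).** For each responder,

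PFS = time to first response + time from first response to progression or death.

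The excess of PFS over duration (with death as an event) is therefore exactly the time to first response:

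- first scheduled scan, week 12 ± 1: 11 to 13 weeks;
- second scheduled scan: about 24 weeks;
- below 11 weeks only if response is first seen on an early unscheduled scan.

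**2. Effect on the median (assumptions mine).** The documents give no expected duration, so I take exponential durations from first response with true median *m* of 12, 24, 36 or 52 weeks, death counted as an event, and no administrative censoring.

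- All respond at week 12: median PFS = *m* + 12.
- 70% respond at week 12 and 30% at week 24: median PFS = *m* · log₂[2(0.7 · 2^(12/m) + 0.3 · 2^(24/m))].

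For *m* = 24 the second formula gives 24 · log₂[2(0.7 × 1.414 + 0.3 × 2)] = 24 · log₂(3.180) = 40.1 weeks.

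**3. Deaths without progression (a separate effect).** Suppose a share *f* of endings are such deaths, at a constant rate. Applying Section 12.3.4 with those deaths censored leaves only the progression hazard, (1 − *f*) of the total, so the median becomes *m*/(1 − *f*). For *m* = 24: 24/0.9 = 26.7 (+2.7) at *f* = 10%, and 24/0.8 = 30.0 (+6.0) at *f* = 20%.

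| True median (weeks) | PFS curve, all respond at week 12 | PFS curve, 30% respond at week 24 | Section 12.3.4, deaths censored, *f* = 10% | Same, *f* = 20% |
|---|---|---|---|---|
| 12 | 24 | 28.5 | 13.3 | 15.0 |
| 24 | 36 | 40.1 | 26.7 | 30.0 |
| 36 | 48 | 51.9 | 40.0 | 45.0 |
| 52 | 64 | 67.8 | 57.8 | 65.0 |

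A simulation of 200,000 durations per setting agrees with these values to within about 0.2 weeks; for instance it gives +2.6 weeks for the 24-week, 10% case.

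The two effects belong to different estimates. PFS counts death, so the PFS columns do not change with *f*. The Section 12.3.4 quantity has no time-origin offset. With a true median of 24 weeks and *f* = 20%, one set of data can yield 24 weeks (death as event), 30 weeks (deaths censored) or 36 weeks (PFS curve, all responding at week 12).

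**The case against.** The strongest defence is that the sentence ties the median and quartiles to Section 12.3.4, whose clock starts at response. On that reading PFS is either loose wording for progression-free time after response, or a supplementary curve, and the reported duration carries no 12-week excess. This stands in part. A reader might infer that the plan has settled on reporting PFS as duration, so that the result is inflated for certain. The text does not say that; the inflation is conditional on reading duration from the PFS curve. But neither benign reading is stated anywhere, and the supplementary-curve reading leaves the endpoint with no named estimator for censored data.

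Three further points against a stronger claim also stand:

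- A reader might add the omission of death to the 12 weeks. The offset comes from the time origin alone, because PFS counts death.
- A reader might take 12 weeks as a minimum. The ± 7-day window allows about 11, and earlier scans are permitted. Those scans are triggered by suspected worsening, so they are unlikely to be where a response is first seen.
- At the 20% response rate sought, 30 × 0.20 = 6 responders are expected. One might say that censoring one death removes one of six events, but that assumes all six would otherwise have an observed event, which nothing in the documents supports.

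Finally, ending duration at progression only is a choice made in sections that Section 12.0 describes as reproducing and paraphrasing RECIST 1.1. It is not an error in itself. What is missing is a rule for deaths. With about six responders the median will be imprecise under any definition, and the plan's futility and efficacy rules use the response rate alone.

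**Conclusion.** The mismatch is real and should be corrected. Section 14.2.3.1 names, as the estimate corresponding to response duration, a quantity that differs from it in both start and event.

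If duration is read from that curve, the excess equals time to first response: about 11 to 13 weeks for responses at the first scheduled scan and about 24 at the second. This needs no assumption beyond the scan schedule. How far it moves the median depends on the mix of response times. In the cases worked above it is 12 weeks if all first respond at week 12, and about 16 weeks if 30% first respond at week 24.

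The silence on death is a second, independent gap affecting only the Section 12.3.4 quantity. Its size rests on an assumed median and an assumed share of deaths without progression, neither of which the documents give.

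The scope is one descriptive secondary endpoint. The primary response-rate analysis, the stopping rules and the PFS analysis in Section 14.2.3.2 are untouched.

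**What to change.** 1. **Section 14.2.3.1:** apply Kaplan-Meier to time from first documented CR or PR to progression or death from any cause, censoring responders without an event at their last disease assessment, and take the median and quartiles from that curve.
2. **Sections 3.2.2 and 12.3.4:** align both definitions with this, so that start, event and censoring rule are the same in all three places. If a progression-only duration is wanted as well, name it separately and state how deaths are treated.
3. **PFS among responders:** drop it, or label it as a separate quantity measured from first treatment.

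The cost is wording only, with no new data, visits or patients. The reported duration may be shorter than a figure read from the PFS curve or one with deaths censored.

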12.0 Assessment of Disease

Patients will be evaluated for response every 12 weeks while on study. If clinicians have clinical concerns, evaluation by imaging may be done as there is clinical or subjective evidence of progression before 12 weeks, with imaging resumed on a Q 12-week imaging cycle. Assessments for response and progression will be carried out according to the Response Evaluation Criteria in Solid Tumors (RECIST) guideline version 1.1¹⁹ which are reproduced and paraphrased in the sections below. Following RECIST criteria, changes in the largest diameter of the tumor lesions and the shortest diameter for malignant lymph nodes will be used.

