12.3.3 Evaluation of best overall response

The best overall response is the best response recorded from the start of the treatment until disease progression/recurrence. The reference for progressive disease is the smallest measurement since treatment initiation. The best response assignment will depend on the achievement of both measurement and confirmation criteria, as seen in the tables below, excerpted from the RECIST v1.1 manuscript ¹⁹.

For patients with measurable disease

Target Lesions	Non-Target Lesions	New Lesions	Overall Response	Best Overall Response when Confirmation is Required*
CR	CR	No	CR	≥4 wks. Confirmation**

CR	Non-CR/Non-PD	No	PR	≥ 4 wks. Confirmation**
CR	Not evaluated	No	PR	
PR	Non-CR/Non-PD/not evaluated	No	PR	
SD	Non-CR/Non-PD/not evaluated	No	SD	Documented at least once ≥ 4 wks. from baseline**
PD	Any	Yes or No	PD	no prior SD, PR or CR
Any	PD***	Yes or No	PD	
Any	Any	Yes	PD	

* See RECIST 1.1 manuscript for further details on what is evidence of a new lesion.
** Only for non-randomized trials with response as primary endpoint.
*** In exceptional circumstances, unequivocal progression in non-target lesions may be accepted as disease progression.

Note: Patients with a global deterioration of health status requiring discontinuation of treatment without objective evidence of disease progression at that time should be reported as "*symptomatic deterioration*." Every effort should be made to document objective progression even after discontinuation of treatment.

For patients with non-measurable disease (i.e. non-target disease)

Non-Target Lesions	New Lesions	Overall Response
CR	No	CR
Non-CR/non-PD	No	Non-CR/non-PD*
Not all evaluated	No	not evaluated
Unequivocal PD	Yes or No	PD
Any	Yes	PD

* 'Non-CR/non-PD' is preferred over 'stable disease' for non-target disease, since SD is increasingly used as an endpoint for assessment of efficacy in some trials, so to assign this category when no lesions can be measured is not advised

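### The planned model of progression by CR, PR and SD fixes neither response timing nor time origin; with best response as a fixed group timed from first treatment, it favours responders even when response has no effect

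*Combined protocol and SAP*

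**What the plan says.** Section 14.2.3.1, in the paragraph on response duration, states that "proportional hazards models will be used to assess whether the rate of disease progression varies materially among the three subgroups of disease response", naming CR, PR and SD, as far as the data allow. It does not say how response enters the model or when the clock starts. The relevant definitions are elsewhere:

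- **Grouping (12.3.3).** "The best overall response is the best response recorded from the start of the treatment until disease progression/recurrence".
- **Confirmation (12.3.3).** The table asks for confirmation of CR and PR at 4 weeks or more. Its footnote reads "Only for non-randomized trials with response as primary endpoint", which describes this trial. SD has only to be "Documented at least once", at least 4 weeks from baseline.
- **Schedule (12.0).** "Patients will be evaluated for response every 12 weeks while on study".
- **PFS clock (12.3.5).** "Progression-free survival defined as the time between the date of first treatment and the date of first documented progression" or death.
- **Duration clocks (12.3.4).** For responders, "The duration of overall response is measured from the time measurement criteria are met for CR or PR". For SD, "Stable disease is measured from the start of the treatment until the criteria for progression are met".

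No other section supplies a landmark, a time-dependent form or a time origin for this comparison.

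**The concern.** A patient's response group is not known when treatment starts. It is settled during follow-up, and progression ends the chance to move to a better group. CR, PR and SD patients have all passed the first scan without progressing, so that interval is common to them. Beyond it, the better groups carry extra guaranteed progression-free time from three sources: the wait for confirmation, responses first seen at week 24 or later, and conversion from PR to CR.

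A model with best response as a fixed group on the PFS clock counts that waiting time as event-free time for responders. This is guarantee-time bias. At stake is the interpretation: the comparison invites the conclusion that response to the combination goes with slower progression, and fitted this way it could not separate a real association from the artefact.

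**Working it through.** **The plan's own figures.** None is given for this analysis. The phase II design figures reproduce and do not depend on it. Early stopping needs 0 of 15 responses: 0.95^15 = 0.463 at a 5% response rate and 0.80^15 = 0.0352 at 20%. Success at 4 or more of 30 has probability 0.058 and 0.865 respectively.

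**Inputs from the documents.** Scans every 12 weeks; confirmation for CR/PR and one assessment for SD; PFS from first treatment; 30 phase II patients; 3 years of data collection (13 scans).

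**Assumptions not in the documents.** Exponential progression, independent of response; median 3, 4 or 6 months; confirmation at the next 12-week scan; response either 20% at the first scan only, or 12% at the first scan and 8% at each later scan with 10% PR-to-CR conversion per scan.

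**Hand check of the mechanism** (median 4 months = 17.33 weeks, responses at week 12 only, confirmed at week 24):

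1. Chance of passing one 12-week interval without progression: q = 2^(−12/17.33) = 0.619.
2. Confirmed responders: q × 0.20 × q = 0.0766 of all patients. SD: 0.6189 − 0.0766 = 0.5423.
3. Progressions found at week 24: q(1 − q) = 0.2359. All fall in SD, because a week-12 responder who progresses then is never confirmed. The interval risk is 0.2359/0.5423 = 0.435 in SD and 0 in responders.
4. After week 24 the risk per interval is 1 − q = 0.381 in both groups.
5. With q² = 0.3830 progressing later (no censoring) and 0.5423 − 0.2359 = 0.3064 SD patients still at risk, the Cox (Breslow) equation for the hazard ratio θ is 1 = 0.2359θ/(0.0766θ + 0.5423) + 0.3830θ/(0.0766θ + 0.3064). At θ = 0.683 the terms are 0.271 + 0.729 = 1.000.

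The true ratio is 1.00 and the model reports 0.68, entirely from the confirmation interval. The same equation gives 0.64 at a 3-month median and 0.75 at 6 months.

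**Simulation under no effect** (200,000 patients per setting; responder-versus-SD hazard ratio at medians of 3 / 4 / 6 months):

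| Setting | PFS clock | Section 12.3.4 clocks |
|---|---|---|
| First scan only, no confirmation | 1.00 / 1.00 / 0.99 | 1.76 / 1.56 / 1.36 |
| First scan only, confirmed | 0.63 / 0.68 / 0.75 | 0.95 / 0.94 / 0.95 |
| Later responses, no confirmation | 0.68 / 0.62 / 0.55 | 1.64 / 1.40 / 1.15 |
| Later responses, confirmed | 0.48 / 0.47 / 0.44 | 0.91 / 0.88 / 0.82 |

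In the last setting on the PFS clock, PR versus SD is 0.51 to 0.52 and CR versus SD is 0.31 to 0.33, so an ordered gradient appears with no effect present.

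**Sensitivity to response timing.** With 20% responding at the first scan and only 2% at each later scan, without confirmation, the ratio is 0.91, 0.86 and 0.83 for medians of 4, 6 and 9 months. Across all variations run, the PFS-clock ratio is about 0.43 to 0.78 with confirmation, and 0.52 to 0.94 without it when later responses occur.

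**Repairs.** A landmark at week 12 or week 24 using status as known at that scan, or a time-dependent covariate, gives 0.99 to 1.01. A week-12 landmark that counts only responders who are confirmed later stays biased, at 0.64 to 0.76.

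**At n = 30** (later responses, confirmed, 3,000 simulated trials), the median hazard ratio is 0.47 / 0.44 / 0.42. A false finding of slower progression (Wald z below −1.96, nominal 2.5%) occurs in 1.8% / 9.1% / 20% of trials where the model can be fitted.

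**The case against.** The text does not say that best response is a fixed baseline factor. A model with a time-dependent covariate is also a proportional hazards model, so a reader who infers that the plan treats response as known at the start is filling a silence. That stands: the defect is an unspecified analysis whose plainest execution is biased.

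A reader might also infer that the hazard ratios must favour CR over PR over SD by construction. The documents do not support that. The first interval is shared; the ratio is 1.00 if all responses come at the first scan without confirmation; and the sentence sits beside the response-duration analysis, whose Section 12.3.4 clocks can put the ratio above 1. The first exception is not available under Section 12.3.3 as written. The second shows that the direction depends on a choice the plan has not made.

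Nor can it be said that the trial would show a false association. At 30 patients a false significant result is far from assured. Confirmation as early as 4 weeks, on an added scan, would also shorten the extra guaranteed time.

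Finally, the comparison is not a listed objective or endpoint, carries no decision rule and is hedged on data availability. That limits its importance. The hedge concerns sparse data, not bias.

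**Conclusion.** The point holds as a gap in specification. Section 14.2.3.1 leaves open how response timing and the time origin are handled. If best response is a fixed group on the PFS clock, the comparison is biased towards responders, with an apparent ratio of about 0.4 to 0.9 when the truth is 1.00. The direction on that clock is the same in every setting with confirmation or later responses. The size rests on assumed medians, response timing and confirmation at the next scheduled scan, so no single figure should be read as the expected bias in this trial. Using the Section 12.3.4 clocks gives 0.82 to 0.95 with confirmation and 1.15 to 1.76 without, so it is no remedy.

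This is a secondary analysis. The primary response rate, the success rule of more than 3 responses and the sample size are untouched. At a 20% response rate, 30 × 0.20 = 6 responders are expected, to be split between CR and PR, so the result can only be exploratory.

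**What to change.** Amend Section 14.2.3.1 to state the time origin and one of the following:

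- **(a) Landmark.** Either the week-12 scan, with response status as known at that scan (unconfirmed, with no use of later confirmation), or the week-24 scan, with status confirmed by then. Include patients progression-free at the landmark and count time from it.
- **(b) Time-dependent covariate.** Response switches on at the date it is established. If confirmed response is used, it switches at the confirming scan and is not back-dated.

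Label the analysis exploratory in either case.

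The cost is wording only, with no new visits, data or patients. The landmark version classes later responders by their landmark status and drops patients who progress before it. Under the assumed 4-month median, about 30 × 0.619 = 18.6 patients would remain at week 12 and 30 × 0.383 = 11.5 at week 24.
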